### **6.1 Summary of findings from non-clinical studies**

The FlowSure team has conducted a non-human study at the cardiology department of the Amsterdam UMC. In the study we have demonstrated the functionality and accuracy of the device in a mock set-up. In the set-up a Braun infusion pump was used to simulate a patient with diuresis and the investigational FlowSure device was tested for operability, accuracy, and safety. The results demonstrated that the measurement with the FlowSure device is more accurate than the Braun infusion pumps that are currently in use in our hospital.

The infusion pump was set at a fixed rate of 50 millilitres per hour. The golden standard is the manual measurement with a measuring cup. The FlowSure accuracy was within 1% margin from the gold standard, whereas the margin for the infusion pump is up to 10%.

### **6.2 Summary of findings from clinical studies**

This will be the first in human study to use the automated urine monitor FlowSure. Therefore, there is no previous experience to draw from, than a comparison with the manual method.

### **6.3 Summary of known and potential risks and benefits**

There is no direct benefit for patients participating in the study. The societal/research benefit of the study lies in the potentially improved diuresis monitoring and registration in the medical record of the patient which will improve the quality and effectiveness of patient monitoring and therefore patient safety.

Risks: The foreseeable added risks associated with the use of the FlowSure in Part A are negligible as using the automated monitor will be additive to the manual measurements.

In part B patient will be monitored with either a manual monitor or the automated FlowSure monitor. If either monitor fails, the hourly urine production can be estimated by dividing the total urine collection since monitoring started by the hours that have passed since insertion of the urine catheter. The nurse will be able to read the urine production manually from the urine collection bag (without the measuring chamber) as the bag is transparent with an approximate graduation scale.

Risk-benefit analysis: Since the expected clinical-scientific benefit of this study is estimated as large and the clinical investigation is, in the opinion of the investigators, proportional to the

added risk associated with the use of the medical device, which is estimated as low, the overall risk-benefit profile of the study is favourable.

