## 1. INTRODUCTION AND RATIONALE

Diuresis, the amount of hourly produced urine, is a vital parameter that is routinely measured in patients hospitalized patients. Up to half of the millions of patients hospitalized each year in nursing wards and all intensive care unit patients and those undergoing surgery have an indwelling urine catheter inserted into the bladder in order to continuously measure urine production. A reduced diuresis of for example less than 30 millilitres per hour is the first sign of hemodynamic and clinical instability of the patient that can be the result of a (occult) bleeding, infection, or heart failure.

The first response of the body to mitigate hemodynamic instability is to retain fluid by decreasing diuresis. The traditional monitors are insufficient as reading and registering diuresis manually every hour for every patient is burdensome for nurses and often deprioritized due to time constraints. Unlike most other vital parameters, diuresis cannot simply be measured instantly like heart rate or blood pressure but requires monitoring over time which complicates registration. Hourly diuresis registration often is incomplete as nurses are unable to register at set times: a nurse assisting one patient cannot register urine production at the same time of the other patients under his or her watch.

As a result, information about the vital parameter diuresis is often not available when the clinical situation of the patient deteriorates and therefore compromising the patient safety. With accurate and complete information regarding changes in diuresis that prompt automated alerts, a clinical deterioration of the patient's condition will be detected earlier and intervened upon sooner, without an extra burden/time costing intervention of the nurse.

The automated FlowSure monitor is a digital hanging scale that continuously weighs urine production over time, as urine flows through the urine catheter into the catheter bag underneath the patient's bed. FlowSure visualizes the most recent hourly urine production on the screen of the medical device and transmits the generated data to the patient's electronic medical record.

Since the specific weight of urine is equal to water and thus one gram is equal to one millilitre, the increase in weight of the urine bag over time is a surrogate for urine production.

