### 7.2 Study procedures

[figure not shown]
In part A, patient with a urine catheter will be monitored using the current standard of care with a manual measuring chamber and a collection bag below the measuring chamber. See image below.

The study procedure in part A is that the manual monitor displayed above will be attached to the investigational FlowSure device. The study subjects will thus be monitored both with the manual monitor and with the investigational FlowSure device.

In part B, in half of the study subject the manual monitor will be replaced by investigational FlowSure device. These patients will receive a urine collection bag without a measuring chamber.

The urine collection bag has an approximate graduation scale, such that in case of device malfunction the nurse can read the urine production from the collection bag.

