**7.6 Premature termination of the study**

The criteria for prematurely terminating the study includes - but are not limited to the following Safety concerns - insufficient or inappropriate device functioning (e.g. when the device produces erroneous measurements that deviate >20% from the golden standard) or regulatory requirements.

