### 10.2 Recruitment and consent

In this clinical study, hospitalized patients with a catheter will be recruited as potential participants. The medical team and research staff will collaborate to identify eligible patients who meet the study's requirements, specifically the inclusion and exclusion criteria. Upon identifying potential participants, the research team will approach them to explain the study's purpose, procedures, potential risks, benefits, and expected outcomes. The initial contact and referral to the research team will be made by the medical team responsible for the patient. The researchers will provide detailed information about the study in a clear and understandable manner, ensuring that all aspects of the study are comprehensively conveyed. Patients will be given ample time to ask questions and seek clarification.

In accordance with ethical guidelines and regulations, the research team will emphasize that participation in the study is voluntary and that patients have the right to decline participation or withdraw at any time without any negative consequences for their medical care.

The informed consent process will be conducted in a private and confidential setting to protect the participants' privacy and ensure a conducive environment for discussion.

Patients who express an interest in participating and meet the eligibility criteria will be provided with a written informed consent form. The research team will thoroughly explain the contents of the consent form, including the study's objectives, procedures, potential risks and benefits, confidentiality measures, and contact information for any questions or concerns. Patients will be encouraged to take their time to review the informed consent form and ask further questions before making a decision. If patients voluntarily decide to participate, they will be asked to sign the informed consent form, indicating their willingness to take part in the study. The research team will emphasize that signing the form does not waive any of their rights and that they can withdraw from the study at any point without penalty. The informed consent process will prioritize patient autonomy, respect for their decision-making capacity, and the protection of their rights and welfare. The research team will ensure that patients fully understand the nature of the study, the potential benefits and risks involved, and their rights as participants.

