#### d. Compatibility with patient population:

The device will be used only in patients who already have, for medical considerations not related to the study, a urine catheter inserted.

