#### f. User training and competence:

Nurses who take care of a study subject will receive written instruction prior to working with the investigational FlowSure device in order to avoid improper use, incorrect interpretations of results, or failure to identify potential risks associated with the device.

g. Maintenance and calibration requirements:

After each deployment the investigational FlowSure device will be checked for adequate function and damage.

h. Environmental considerations:

The housing of the device is waterproof and fully reusable.

i. Potential for misuse or user error:

The potential for misuse or error are small. The software of the investigational FlowSure device is programmed to recognize when the collection bag is emptied by the nurse and simply asks them to confirm their action. If the bag is removed from the device for a period of time and then placed back, the device will recognize this and continue its measurements.

Incorrect measurements as a result of swinging of the urine collection bag is mitigated by the software algorithm through discarding large changes in subsequent measurements.

A potential for misuse is when the urine collection bag touches the ground and the bag does not hang on the device, the measurements are inadequate. Nurses are instructed to make sure that urine collection bag does not touch the ground.

j. Mitigation strategies and safety features:

If the investigations FlowSure device malfunctions or fails, the nurse can always revert back to reading the urine production manually from the urine collection bag (without the measuring chamber) as the bag is transparent with an approximate graduation scale.

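### The Part B fallback for hourly urine output counts volume from the start of monitoring but hours from catheter insertion, so in the FlowSure arm it reads too low

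*Combined protocol and SAP*

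**What the plan says.** The Summary (Risks) and Section 6.3 describe the same fallback for Part B, in the same words. Section 6.3 reads "If either monitor fails, the hourly urine production can be estimated by", followed by "dividing the total urine collection since monitoring started by the hours that have passed since insertion of the urine catheter".

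Other sections fix the order of events in the FlowSure arm:

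- Section 10.2: "hospitalized patients with a catheter will be recruited as potential participants".
- Structured Risk Analysis, item d: "The device will be used only in patients who already have, for medical considerations not related to the study, a urine catheter inserted".
- Section 7.2: in this arm FlowSure takes the place of the manual monitor, and the bag changes too: "These patients will receive a urine collection bag without a measuring chamber".

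The protocol also offers a second back-up, reading the graduated collection bag directly. Section 6.3 adds it after the formula. Sections 7.2 and 10.3 and items e and j of the Structured Risk Analysis name it alone; item j says "the nurse can always revert back to reading the urine production manually from the urine collection bag". The Summary's risk paragraph gives only the formula.

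**The concern.** A mean hourly rate needs a volume and a duration taken over the same window. Here the volume runs from the start of monitoring and the duration from catheter insertion. Where the catheter was in place first, the denominator is too long and the rate too low.

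What is at stake is a bedside value for a patient whose monitor has failed. The error always runs towards the level the protocol treats as a warning. Section 1 states: "A reduced diuresis of for example less than 30 millilitres per hour is the first sign of hemodynamic and clinical instability". A patient with adequate output could therefore appear oliguric. No trial result is at stake.

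**Working it through.** The plan gives no numerical example of the fallback, so there is no figure to reproduce. The check is algebra.

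**Inputs**

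- M, hours from the start of monitoring to the failure. Section 3 caps study duration at 24 h. I use 8 h and 24 h, the two intervals named in Section 7.1.1.
- P, hours from catheter insertion to the start of monitoring. The documents do not give it. Assumed values: 1, 2, 6 and 12 h.
- V, urine collected during the M hours.
- d = V/M, the true mean hourly output over the monitored window. Assumed where needed: 50 and 100 mL/h.
- Yardsticks: 30 mL/h (Section 1) and 20% (Section 7.6).

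**Formula**

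- Plan's estimate: V/(M+P).
- Ratio to the true mean: [V/(M+P)] / [V/M] = M/(M+P).
- Relative under-reading: 1 − M/(M+P) = P/(M+P).

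V cancels, so the ratio does not depend on the true rate or on the flow being constant. At P = 0 there is no error.

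**Under-reading, P/(M+P)**

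| P (h) | M = 8 h | M = 24 h |
|---|---|---|
| 1 | 1/9 = 11% | 1/25 = 4% |
| 2 | 2/10 = 20% | 2/26 = 8% |
| 6 | 6/14 = 43% | 6/30 = 20% |
| 12 | 12/20 = 60% | 12/36 = 33% |

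For a given P, the error is larger when the failure comes early.

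**When the under-reading exceeds 20%**

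P/(M+P) > 0.20 gives P > M/4: more than 2 h at M = 8, or more than 6 h at M = 24. Section 7.6 cites, as an example of unacceptable device functioning, the case "when the device produces erroneous measurements that deviate >20% from the golden standard". That limit was not written for the fallback; it serves here only for scale.

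**When the estimate falls below 30 mL/h**

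d × M/(M+P) < 30 gives P > M × (d/30 − 1).

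| True mean d | M = 8 h | M = 24 h |
|---|---|---|
| 50 mL/h | 8 × 0.667: P > 5.3 h | 24 × 0.667: P > 16 h |
| 100 mL/h | 8 × 2.333: P > 18.7 h | 24 × 2.333: P > 56 h |

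Example: d = 50 mL/h, M = 8 h and P = 12 h give V = 400 mL. The rule returns 400/20 = 20 mL/h; the matched calculation returns 400/8 = 50 mL/h.

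**The case against.** The strongest reply is that the start of monitoring is not defined. Section 1 describes catheters as being placed so that urine production can be measured continuously, and Section 7.2 has FlowSure replacing a manual monitor already in use. If monitoring means all diuresis monitoring since insertion, and earlier volumes are counted, the two clocks agree. This reading fits Section 6.3 poorly. The sentence just before the formula speaks of monitoring with the manual or FlowSure monitor assigned in Part B, and the FlowSure arm changes to another bag. Even on this reading the proposed wording does no harm. The point does hold for the manual arm: if monitoring there began at insertion, the windows coincide and there is no error.

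Several other points stand and limit the importance:

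- The estimate is optional and appears only in the risk text; the study procedures in Section 7.2 rely on reading the bag.
- It enters no endpoint, sample size or analysis.
- P is unknown, and with a short P and a long M the error is small (4% at P = 1 h, M = 24 h).
- The mismatch produces false low readings. It does not hide a true low output, and staff alerted by it can check the bag.
- The ratio concerns the mean over the monitored window. Any cumulative average can also miss the current hour's output, and aligning the clocks does not cure that.

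**Conclusion.** The concern holds. As written, the fallback in the FlowSure arm returns M/(M+P) of mean output over the monitored window and is too low whenever P > 0. For assumed P of 1 to 12 h the under-reading is 11% to 60% at M = 8 h and 4% to 33% at M = 24 h.

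The direction of the error rests on the protocol's own sequence (catheter first, FlowSure and its bag afterwards) and on taking monitoring to mean the monitor assigned in Part B. The size rests on P, which is assumed. In the manual arm the error arises only if monitoring began after insertion. This is a low-impact correction to a patient-monitoring instruction; it does not threaten the trial's conclusions, but it should be made.

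**What to change.** In the Summary (Risks) and in Section 6.3, change the denominator to the hours since monitoring started, and state that the volume includes any urine emptied during that window. The estimate then equals V/M, a ratio of 1.00 to the true mean over the window, in both arms and for any P. The cost is one phrase in two places, with no extra data, time or burden on patients.

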## 7. METHODS

[figure not shown]
### 7.1 Study parameters/endpoints

#### 7.1.1 Main study parameter/endpoint

The primary outcome event in Part A will be the accuracy of urine measurement over two set time intervals (a nursing shift of 8 hours and a full 24-hours period) using manual monitoring and automated monitoring. The golden standard is the total urine production measured in a measuring cup by draining the collection bag in comparison with the new FlowSure device. The primary outcome in part B of the study will be the completeness of the hourly diuresis registration will be compared between the manual and automated measurement groups.

### 7.2 Study procedures

[figure not shown]
In part A, patient with a urine catheter will be monitored using the current standard of care with a manual measuring chamber and a collection bag below the measuring chamber. See image below.

The study procedure in part A is that the manual monitor displayed above will be attached to the investigational FlowSure device. The study subjects will thus be monitored both with the manual monitor and with the investigational FlowSure device.

In part B, in half of the study subject the manual monitor will be replaced by investigational FlowSure device. These patients will receive a urine collection bag without a measuring chamber.

The urine collection bag has an approximate graduation scale, such that in case of device malfunction the nurse can read the urine production from the collection bag.

### 7.3 Withdrawal of individual subjects

Subjects can leave the study at any time for any reason if they wish to do so without any consequences. The investigator can decide to withdraw a subject from the study for urgent medical reasons. All data up until the point of withdrawal can be used

### 7.4 Replacement of individual subjects

Subject who withdraws consent, will be replaced until the sample size of the study has been reached without changing the randomization parameters, there will be no reuse of previous allocations. In addition, participants may also be replaced in cases where the primary endpoint cannot be evaluated due to demonstrable deviations from study procedures. Such cases include, but are not limited to:

- Disposing of the reference standard prematurely without the presence of a study investigator
- Demonstrably incorrect handling or operation of the investigational device.

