### 3. STUDY DESIGN

The study will consist of two parts. Part A is single arm intervention study in which patients will receive both the manual monitors and automated FlowSure monitor (both devices will be used in conjunction). Part B is a two-arm randomized non-blinded intervention study in which patients will be monitored with either the manual monitoring or automated FlowSure monitoring.

In both part A and part B the study will last for duration that the patient has a urine catheter inserted with a maximum of 24 hours. The setting of the study will be hospitalized patients who - for medical reasons unrelated to the study - have a urine catheter inserted.

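### Replacing patients for mishandled FlowSure devices can become a one-arm exclusion in the randomised comparison of Part B

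*Combined protocol and SAP*

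**What the plan says.** Section 7.4 has two replacement rules. The first covers patients who withdraw consent: they are replaced until the planned number is reached, the randomisation settings stay as they are, and "there will be no reuse of previous allocations". The second is permissive: "participants may also be replaced in cases where the primary endpoint cannot be evaluated due to demonstrable deviations from study procedures". Two examples follow, in a list that is expressly not exhaustive. One is early disposal of the reference standard. The other is "Demonstrably incorrect handling or operation of the investigational device". Neither rule names a part of the study.

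Section 3 describes Part B as a "two-arm randomized non-blinded intervention study", and section 7.2 says that "in half of the study subject the manual monitor will be replaced by investigational FlowSure device". The manual arm of Part B therefore has no investigational device.

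Section 9.2 defines the Part B outcome as the share of hourly measurements that are recorded, judged from the electronic record, and presents it as an indicator of reliability and usability, among other things. Section 9.1 gives a comparison of two proportions by chi-square or Fisher's exact test. Neither subsection defines an analysis set or mentions replaced patients. The nearest rule is in section 7.3: "All data up until the point of withdrawal can be used". It concerns withdrawn subjects and permits use of their data without requiring it.

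**The concern.** In Part B an hour lost because the device was used wrongly is part of what is being measured. If the patient stays in the analysis, that hour counts against FlowSure. If the patient is replaced and left out, it disappears. A missed nurse reading in the manual arm simply counts as incomplete, and the named handling ground has no counterpart there.

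Leaving such patients out would be an exclusion after randomisation, confined to one arm, related to the outcome, and decided with the arm known. Section 8.5 provides no data safety monitoring board and section 11.2 no formal monitoring, so no independent check on these decisions is described. Part B is the only randomised comparison in the study. Section 11.1 foresees sharing coded data to obtain certification, so the size of the estimate matters as well as the p-value.

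**Working it through.** **Does the rule reach Part B?** Section 7.4 speaks of randomisation and earlier allocations, and only Part B is randomised, so the section as a whole covers Part B. The reference-standard example fits the measuring-cup comparison of Part A. The handling example fits either part and carries no limit.

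**Does anything keep replaced patients in the analysis?** The clause on not reusing allocations belongs to the consent-withdrawal sentence and concerns the randomisation list. Section 7.3 concerns withdrawal. Section 9 is silent. The question is left open.

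**Inputs from the documents.** 25 patients per arm (4.3); completeness 50% manual and 90% FlowSure (4.3 and 9.2; the plan says above 90%, and 90% is used here); monitoring "with a maximum of 24 hours" (3); "a nursing shift of 8 hours" as a natural block of lost time (7.1.1). The plan's own difference is 0.90 − 0.50 = 0.40, or 40 points.

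**Assumptions.** The documents give neither the share q of FlowSure patients mishandled and dropped nor their completeness c. I take q = 4% (1 in 25) and 10%, c from 0 to 0.90, and 24 monitored hours per patient.

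**Formula.** Mean with all randomised patients kept = q·c + (1 − q)·0.90. Overstatement if the mishandled are dropped = 0.90 minus that mean = q·(0.90 − c).

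**One patient in 25, in hours.** The arm has 25 × 24 = 600 patient-hours, and one patient is expected to contribute 24 × 0.90 = 21.6 recorded hours.

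- No hours recorded: 21.6 lost; 21.6/600 = 3.6 points.
- Half recorded (12 hours): 9.6 lost; 9.6/600 = 1.6 points.
- One 8-hour shift unrecorded: 8 × 0.90 = 7.2 lost; 7.2/600 = 1.2 points; c = 14.4/24 = 0.60.
- All hours recorded as usual: 0 lost; 0 points.

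| Completeness c of mishandled patients | Overstatement, q = 4% | Overstatement, q = 10% | Difference from manual with all kept, q = 4% | Same, q = 10% |
|---|---|---|---|---|
| 0 | 3.6 | 9.0 | 36.4 | 31.0 |
| 0.50 | 1.6 | 4.0 | 38.4 | 36.0 |
| 0.60 | 1.2 | 3.0 | 38.8 | 37.0 |
| 0.90 | 0.0 | 0.0 | 40.0 | 40.0 |

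All entries in the last four columns are percentage points.

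**Counting the replacement as an extra randomised patient.** With k patients dropped and 25 others retained, the overstatement is k·(0.90 − c)/(25 + k). For k = 1 this gives 0.90/26 = 3.5, 0.40/26 = 1.5 and 0.30/26 = 1.2 points for c = 0, 0.50 and 0.60. The change is trivial.

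**Would significance survive?** Section 9.1 does not fix the unit of analysis, so several tests were simulated with all randomised patients kept: 25 against 25 patients, 50% against 90%, beta-binomial hours, and within-patient correlations (manual/FlowSure) of 0.1/0.1, 0.3/0.1 and 0.5/0.3, over every q and c in the table. There were 10,000 trials per setting (3,000 for Mann-Whitney). The share of trials finding FlowSure significantly better was 0.996–1.000 for chi-square on pooled hours (which ignores clustering), 0.923–1.000 for Mann-Whitney on patient values, and 0.865–1.000 for Welch's test on patient values. The lowest values came at q = 10%, c = 0 and correlations 0.5/0.3.

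**The case against.** The strongest reply is that the rule's own condition closes this route. Replacement is allowed only when the endpoint cannot be evaluated, and in Part B a missing hour can be evaluated: it is not registered. On that reading both examples belong to Part A. The deviation must also be demonstrable, which is a test of evidence, and the general ground of procedural deviation could apply to the manual arm too. This is the sensible reading and it narrows the problem. It is not what the text secures, because 7.4 lists device mishandling, without limit, among the cases that qualify.

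The harm also needs a chain of events: mishandling in Part B, a judgement that the patient cannot be evaluated, replacement, omission from the analysis, and hours actually lost. No passage says that replaced patients are omitted. That is why the conclusion is conditional.

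On size, section 11.7(i) calls the potential for misuse small. The one misuse it describes, a bag resting on the ground, gives inadequate measurements and is not said to give missing ones; that is the zero-overstatement case. The software is said to resume after the bag is taken off and put back, and nurses can read the graduated bag if the device fails, although it is unclear whether such readings count as registrations under 9.2. The figures for c = 0 are therefore an outer bound.

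A single sentence could close the core gap. The further rules proposed below are short and make that sentence workable.

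**Conclusion.** The concern holds. As written, 7.4 allows a discretionary replacement on a named ground that only the FlowSure arm of Part B can meet, and section 9 does not keep the replaced patient in the comparison. If such patients are dropped, completeness is overstated by q·(0.90 − c): nothing where mishandled hours are still recorded, 1.2 points where one patient in 25 loses a shift, and at most 3.6 points (4% mishandled) or 9.0 points (10%). A reported difference of 40 points would then be 36.4–40 or 31–40 with everyone kept. Both q and c are assumptions. The effect is mainly an inflated estimate: at least 86% of simulated trials still found FlowSure better with all patients kept. It should be fixed because it touches the only randomised comparison and the fix is cheap. Confidence is medium, since the harm depends on how the team would apply an ambiguous rule.

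**What to change.** In 7.4, limit the grounds of lost reference standard and device mishandling to Part A. For Part B, add to 7.4 and section 9:

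- The primary analysis includes every randomised patient in the assigned arm.
- Any hour of the monitoring period (catheter in place, up to 24 hours) without a registration in the electronic record counts as not registered, in both arms and whatever the cause.
- Withdrawn patients contribute their hours up to withdrawal where 7.3 allows.
- Additional patients receive new random allocations and are added to the randomised set; they do not take the place of earlier patients.
- Replacements are reported by arm with reasons. Any analysis without mishandled patients is a sensitivity analysis only.

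The cost is wording in two places and a protocol amendment, to be notified to the ethics committee and the competent authority if it is substantial (11.3). FlowSure completeness may come out slightly lower, and a few patients beyond 50 may be analysed.
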